10.6.2 Analyses of Exploratory Endpoints

Overall Response Rate (CR+PR) after blinatumomab treatment based on Lugano criteria ([Appendix C](#)) will be presented using the same methods as the secondary ORR endpoint.

Graphical summaries of changes from baseline over time in biomarker levels may be provided. Association between baseline levels or presence of tumor biomarkers will be explored graphically for ORR and PD effects.

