- k **Creatinine clearance to be calculated by Cockcroft-Gault equation.**
- l Lymphocyte subsets for the study are listed above in SOA and are to be collected prior to administration of IP on days 1 and 22, however, additional samples will be collected for adverse events of CTCAE  $\geq$  grade 3 neuro toxicity and CRS occurs throughout the study at the start and resolution of the event (**refer to Section 7.3.16.1**).
- m Disease assessments are to be performed to establish staging and response per Cheson **if disease assessment is by CT scans (Appendix A)** and Lugano criteria **if disease assessment includes PET/CT (Appendix B)**. For PET-CT, CT, or contrast enhanced CT the same imaging modality should be used throughout the study for an individual subject. Disease assessment to occur: during screening; just prior to optional cycle 2 if given (attempt to obtain this study at least 2 weeks after stopping IP in cycle 1 and just prior to starting cycle 2); and the last disease assessment is 4 weeks after finishing the last dose of IP. If PET and CT are acquired on the same day, it is strongly recommended that PET is performed prior to the CT with IV contrast.
- n Bone marrow biopsy to be performed according to Cheson ([Appendix A](#)) and Lugano criteria ([Appendix B](#) [standard of care per investigator]).
- o Bone marrow biopsy performed within 21 days of the first dose of IP may be used in place of screening assessment to establish staging or response per Cheson ([Appendix A](#)) and Lugano criteria ([Appendix B](#)).
- p Anti-blinatumomab antibody predose on day 1, before the administration of first SC dose (following 12 hour wash out from cIV), and predose at the re-start of cIV infusion (following the 2 to 3 day washout).
- q **Cytokine sample on days 1 and 22: predose and at the following time points postdose, 2 hours ( $\pm$  15 minutes), 4 hours, 6 hours ( $\pm$  30 minutes for both the 4 and 6 hour time points), and 12 hours (before the next injection in case of q12h dosing  $\pm$  1 hour). Additional samples will be collected for adverse events of CTCAE  $\geq$  grade 3 neuro toxicity and CRS occurs throughout the study at the start and resolution of the event (Refer to [Section 7.3.16.2](#)).**

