2.3 Exploratory Objective

- To determine the pharmacodynamics (PD) time profiles for B- and T-lymphocytes as well as cytokine profiles during SC administration.
- To evaluate efficacy response following treatment with SC blinatumomab administration using Lugano criteria if positron emission tomography-computed tomography (PET/CT) is used for evaluation ([Appendix B](#))

3. Study Overview

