7.1 Full Analysis Set

All subjects who receive blinatumomab are included in the full analysis set (FAS). This definition is in line with the intent-to-treat (ITT) principle in single-arm open-label studies. For the dose escalation part of the study subjects will be analyzed according to the initial blinatumomab dose received. For the dose expansion, subjects will be analyzed according to the dose selected for this part of the study.

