10.6 Efficacy Analyses

Statistical analyses of efficacy endpoints will be considered secondary. Efficacy data will be conducted on the Full Analysis Set.

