10.6.1 Analyses of Secondary Efficacy Endpoint(s)

The efficacy endpoint of the study is ORR (CR+PR) after blinatumomab treatment based on [Chesons' 2007](#) criteria ([Appendix B](#)). The analysis is based on the response evaluation recorded in the CRF for subjects in the full analysis set. Subjects will be considered as non-responders if there is no response assessment available. The rate will be estimated along with its 95% Clopper-Pearson exact confidence interval by dose group and overall. Subject listings with related collected parameters will also be provided.

Summary of other best responses status by each response category will be also provided. The number and percentage of subjects with a disease response of complete response (CR), partial response (PR), stable disease (SD) or progressive disease (PD) will be presented for the dose escalation and/or expansion parts of the study.

Subject listings with related collected parameters will also be provided.

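### The exploratory Lugano ORR has no PET/CT denominator, so CT-only subjects with no Lugano category recorded would count as failures

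*SAP*

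**What the plan says.** SAP 10.6.2 gives the Lugano ORR no method of its own; it "will be presented using the same methods as the secondary ORR endpoint". The methods it borrows are in SAP 10.6 and 10.6.1:

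- Population: "Efficacy data will be conducted on the Full Analysis Set". SAP 7.1 defines that set as everyone who receives blinatumomab, whatever scan was used.
- Source: "The analysis is based on the response evaluation recorded in the CRF for subjects in the full analysis set".
- Missing response: "Subjects will be considered as non-responders if there is no response assessment available".
- Presentation: the rate with its Clopper-Pearson 95% "exact confidence interval by dose group and overall".

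The Lugano measure itself is conditional. The objective in SAP 2.3 (and Protocol 1.3) is to evaluate response "using Lugano criteria if positron emission tomography-computed tomography (PET/CT) is used for evaluation". Protocol Table 3 footnote m, for Period 1, likewise ties Lugano to assessments that include PET/CT and Cheson to CT. The Lugano table in SAP Appendix C contains only PET-based categories.

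CT alone is permitted. Inclusion criterion 105 accepts measurable disease on PET-CT or CT, the synopsis leaves imaging to standard of care, and the schedules ask that each subject keep one modality throughout.

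Other places name Lugano with no PET/CT condition: SAP 4.1.3, the best-overall-response definition in SAP section 6, Protocol 10.1.1.3, Protocol 7.3.10, Table 5 footnote k and Table 7 footnote i.

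**The concern.** A subject imaged by CT throughout, as the protocol allows, cannot be classified from the PET-based Lugano table. For such a subject the Lugano response is not applicable, which differs from missing. The borrowed non-responder rule does not distinguish the two, and no section turns the PET/CT condition into an analysis set or denominator.

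For the subjects affected, the Lugano ORR would then reflect which scan the site used as well as whether the lymphoma responded. It could fall below the Cheson ORR for that reason alone, and a reader comparing the two could take the gap for a difference in response. Because the rate is also given by dose group, in cohorts of about 6 and an expansion of up to 15, a few CT-only subjects could move it visibly.

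**Working it through.** The plan states no expected Lugano ORR, PET/CT share or precision target, so there is no figure to reproduce. The check traces the rule and then shows its effect over a range of assumptions.

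**Tracing the rule for a CT-only subject**

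1. The subject received blinatumomab and so is in the full analysis set (SAP 7.1), which is the efficacy set (SAP 10.6).
2. SAP section 7 makes that set the default unless something else is noted. Nothing is noted for Lugano in SAP 4.1.3, 7 or 10.6.2.
3. Suppose no Lugano category is on the CRF. If the missing-response rule is read as referring to a Lugano assessment, the subject is a non-responder by rule. If it is read as any response assessment, the subject's Cheson assessment means that the rule is not triggered, but the subject is still in the denominator with no Lugano CR or PR. The rate is the same either way.
4. If a site does enter a Lugano category from CT, that category is used and the effect does not arise for that subject.

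**Formula under the condition in step 3**

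Let N be the full analysis set, n the number assessed by PET/CT, and x the Lugano responders among them. Write r = x/n and q = n/N. The reported rate is x/N = (x/n) × (n/N) = r × q.

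**Expected reported rate (r and q are assumptions)**

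| PET/CT share q | r = 60% | r = 40% |
|---|---|---|
| 25% | 15% | 10% |
| 50% | 30% | 20% |
| 75% | 45% | 30% |
| 90% | 54% | 36% |
| 100% | 60% | 40% |

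**With Clopper-Pearson 95% intervals**

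The 54 is the approximate enrollment in SAP 3.2, used here as an illustrative full analysis set, with r about 60%.

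- q = 50%: n = 27, and 27 × 0.6 = 16.2, so x = 16.
- q about 90%: 54 × 0.9 = 48.6, so n = 49; 49 × 0.6 = 29.4, so x = 29.
- One cohort of 6 with 3 subjects on PET/CT and 2 responders.

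| Case | Full-analysis-set denominator | PET/CT denominator |
|---|---|---|
| 54 treated, 27 on PET/CT | 16/54 = 29.6% (18.0 to 43.6) | 16/27 = 59.3% (38.8 to 77.6) |
| 54 treated, 49 on PET/CT | 29/54 = 53.7% (39.6 to 67.4) | 29/49 = 59.2% (44.2 to 73.0) |
| Cohort of 6, 3 on PET/CT | 2/6 = 33.3% (4.3 to 77.7) | 2/3 = 66.7% (9.4 to 99.2) |

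The shift in the second row is 59.2 − 53.7 = 5.5 percentage points.

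**The case against.** The strongest reply is that the SAP already contains the condition. SAP 2.3 limits the Lugano objective to PET/CT, and an endpoint can be read under its own objective, leaving CT-only subjects outside the evaluation. That is a reasonable reading of intent, but the objective defines no denominator, the endpoint wording does not repeat it, and the method sections point to the full analysis set. It weakens the point without removing it.

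A second reply is that a CT-only subject does have a response assessment, by Cheson. As shown above, this does not help, since the subject remains in the denominator without a Lugano response.

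Three limits do stand. First, a reader might infer that CT-only subjects are certain to be scored as failures. The documents do not support that: the CRF is not available, and the passages that name Lugano unconditionally could lead a site to enter a category from CT. Second, a reader might infer that the Lugano ORR will be roughly halved. That needs about half the subjects to be CT-only, and nothing in the documents gives that share. PET-CT is listed first among the modalities, and Table 7 footnote j lets a negative PET replace marrow biopsy, so substantial PET use seems expected. Third, counting missing as failure is a normal conservative convention, and the CR, PR, SD and PD counts and listings would expose a shortfall against the denominator. The counts alone, however, would not separate CT-only subjects from PET/CT subjects who missed follow-up.

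**Conclusion.** The point holds conditionally and is minor. As written, SAP 10.6.2 applies a full-analysis-set, missing-is-failure rule to a measure that the objective and Table 3 footnote m confine to PET/CT, in a trial that allows CT alone. Where no Lugano category is recorded for CT-only subjects, the reported rate is the PET/CT-subject ORR multiplied by the PET/CT share. The size is unknown, since neither factor is in the documents: zero at a 100% share, about 5 to 6 points at a 90% share with a 60% ORR, and larger at lower shares.

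It would go too far to infer any effect on the trial's main conclusions. The endpoint is exploratory, and no test, sample size or dose decision rests on it. The Lugano denominator does not alter the DLT rules or the Cheson ORR.

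**What to change.** **In SAP 10.6.2:**

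- Set the Lugano ORR denominator to full-analysis-set subjects with a baseline PET/CT.
- Within that set, count subjects with no follow-up response assessment as non-responders.
- Report separately the number of CT-only subjects and the number with baseline PET/CT but CT-only follow-up. The second group remains in the denominator, so its count shows how far scan choice could still affect the rate.
- The full-analysis-set rate may be kept as a sensitivity analysis.

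**Elsewhere:** add the same PET/CT condition in SAP 4.1.3, the SAP section 6 best-overall-response definition, Protocol 10.1.1.3, Protocol 7.3.10, Table 5 footnote k and Table 7 footnote i. Amending only some of these would leave the conflict in place.

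**Optional:** if Table 3 footnote m is also edited so that Cheson is scored whatever the modality, give the reason. As worded it ties Cheson to CT, so PET/CT subjects could lack the Cheson category that the secondary ORR needs. The Cheson appendix already contains PET rules.

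**Cost:** wording only, with no new data. The denominator shrinks and intervals widen: in the illustration, 27 instead of 54 subjects gives a width of 38.8 instead of 25.6 points. By dose group they become very wide; 2/3 spans 89.7 points against 73.4 for 2/6.

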10.7 Pharmacokinetic Analysis

The PK analysis will be based on the PK analysis set described in [section 7.4](#). Blinatumomab serum concentration-time data will be used to determine the PK parameters under cIV and subcutaneous administration, respectively, using non-compartmental methods and will be listed for individual subjects. All concentration values below the quantifiable limits were set to zero before pharmacokinetic analysis. Actual dose and actual sampling time will be used for PK analysis. Summary statistics, including mean, standard deviation, median (range), geometric mean and CV% of geometric mean will be computed for each pharmacokinetic parameter and grouped by dose, period and route of administration. Individual concentration-time data will be tabulated and presented graphically. Mean concentration-time profiles for each dose will be provided.

The following PK parameters will be estimated:

- The steady state serum concentration (C_{ss}) under continuous IV infusion (cIV), summarized as the observed concentrations collected after 5 half-lives after the start of the IV infusion of each dose (ie, 9, 28 and 112 $\mu\text{g}/\text{day}$).
- Systemic clearance (CL) following cIV; calculated as $CL=R_0/C_{ss}$; where R_0 is the infusion rate ($\mu\text{g}/\text{hr}$) and C_{ss} is the average C_{ss} . Both R_0 and C_{ss} were dose-normalized to 112 $\mu\text{g}/\text{day}$ for this calculation.
- The maximum observed blinatumomab concentration (C_{max}) after subcutaneous administration
- The time (t_{max}) at which C_{max} occurred after subcutaneous administration
- The area under the concentration-time curve (AUC) after the first and the last subcutaneous doses for a dosing interval τ (AUC_{τ}); estimated using the linear trapezoidal method; where τ is a dosing interval (eg, 12 hr or 24 hr)
- C_{min} , defined as trough concentration at 12 hrs for q12h regimen or at 24 hrs for q24h regimen after subcutaneous administration
- The apparent clearance (CL/F) after subcutaneous dosing; calculated as $CL/F = \text{Dose}_{sc} / AUC_{\tau-ss}$ (at steady state)
- The volume of distribution based on terminal phase (V_z/F) after subcutaneous administration; calculated as $V_z/F = CL/F / \lambda_z$, where λ_z was the first-order rate constant estimated via linear regression of the terminal log-linear decay phase as determined from the noncompartmental analysis

- Terminal half-life ($t_{1/2,z}$) after subcutaneous administration; calculated as $t_{1/2,z} = \ln(2) / \lambda_z$
- Accumulation ratio after subcutaneous administration, calculated as the ratio of AUC_{τ} (last dose) / AUC (first dose)
- Bioavailability (F); calculated as $F = (CL * AUC_{\tau-ss}) / Dose_{sc}$

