## 2.3 Dose Selection

### 2.3.1 Pharmacokinetics

The PK of blinatumomab was assessed over a dose range from 5 to 90 µg/m^2/day following cIV administration in subjects with NHL. Mean concentration of drug at steady state values increased dose-proportionally over the dose range tested. The estimated mean clearance, volume of distribution, and terminal half-life were 2.29 L/hour, 4.84 L and 2.47 hours, respectively, in subjects with NHL (Study MT103-104 [Goebeler et al, 2016]). Since body size (weight or body surface area [BSA]) was not a factor affecting the blinatumomab PK, a fixed dosing regimen, instead of BSA based

Approved

dosing, is appropriate for the treatment in adults. The fixed dosing regimen has been tested in Study MT103-208 (Viardot et al, 2016) in patients with diffuse large B-cell lymphoma and showed comparable exposure levels as those with an equivalent BSA based regimen.

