## 2.4 Rationale

[figure not shown]
The effect of blinatumomab in the treatment of NHL was tested in a dose escalation study (Study MT103-104 [Goebeler et al, 2016]). A dose dependent clinical response was observed and objective clinical responses were seen starting at 15  $\mu\text{g}/\text{m}^2/\text{d}$  (~28  $\mu\text{g}/\text{day}$ ) and peaked at 60  $\mu\text{g}/\text{m}^2/\text{d}$  (~112  $\mu\text{g}/\text{day}$ ). Due to transient cytokine release after initiation of treatment, a step-dosing regimen was implemented to minimize cytokine related adverse events. An effective step-dose regimen of 9  $\mu\text{g}/\text{d}$  (week 1)-28  $\mu\text{g}/\text{d}$  (week 2)-112  $\mu\text{g}/\text{d}$  (remaining weeks) following cIV infusion for 8 weeks was established for the treatment of diffuse large B-cell lymphoma in study MT103-208 (Viardot et al, 2016). In this study, the blinatumomab concentration levels following the cIV regimen will be used as a reference to guide dose selection of SC administration. The target SC dose for the treatment of NHL is a dose that can achieve a similar exposure (area under the curve) as that of 112  $\mu\text{g}/\text{d}$  dose under cIV. To facilitate the SC dose selection, PK simulation was performed with the PK parameters (clearance and volume of distribution) generated from human studies under cIV and an assumed bioavailability of 0.25 in humans which was an approximate average of bioavailability in mouse (0.35), rat (0.16), monkey (0.21) and pig (0.30) under SC administration.

The simulated PK profiles of cIV (9/28/112  $\mu\text{g}/\text{d}$ ) and SC every day (112/450) and twice a day ([BID] 56/225  $\mu\text{g}/\text{dose}$ ) are provided in Figure 3. Based on currently available information on bioavailability and exposure, 450 (or 225  $\mu\text{g}/\text{BID}$ ) is the estimated SC equivalent dose to the cIV 112  $\mu\text{g}/\text{d}$  dose.

The assumption will be examined in Period 1 of this study following the PK assessment in the cIV run-in phase and then SC administration.

The calculated bioavailability for SC administration, the PK profiles of SC as well as safety and tolerability data will be used to assess the doses recommended for the Period 2 of the study.

**Figure 3. Simulated Blinatumomab Concentration-time Profiles Under Continuous IV Infusion and Under Once (1a) or Twice (1b) Daily Subcutaneous Administrations**

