9.3 Handling of Missing and Incomplete Data

The following imputation of missing values will be done:

- Incomplete adverse event and concomitant medication dates will be imputed as per [Appendix A](#)
- No data imputation for PK and biomarker data.

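### Zeroing below-quantification infusion samples can inflate a subject's clearance and bioavailability by 33% to 50%; the linear trapezoid separately adds a modest, interval-dependent AUC bias

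*SAP*

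**What the plan says.** SAP 10.7 lays down one rule for unquantifiable (BLQ) samples, without regard to route: "All concentration values below the quantifiable limits were set to zero before pharmacokinetic analysis". Interval AUC after SC dosing is "estimated using the linear trapezoidal method". Clearance under infusion is CL = R0/Css with an average Css, and "Both R_0 and C_{ss} were dose-normalized to 112" µg/day. The SAP then defines "Bioavailability (F); calculated as" CL × AUCτ,ss/Dose_sc, so any proportional error in CL or in AUC passes straight into F.

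Protocol 7.3.15.1 takes one infusion sample at each run-in level (days 2, 9 and 16, at 9, 28 and 112 µg/day) and one more on day 30 after 112 µg/day is resumed. Protocol 2.4 and 3.1.2 use the calculated bioavailability, together with PK profiles, safety and DLRT review, to derive the Period 2 SC doses. Neither document gives a lower limit of quantification (LLOQ).

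**The concern.** A zero is a reasonable stand-in for a sample drawn before any drug is on board. It is not one for a sample drawn during a constant infusion at steady state, where a BLQ result means low, not absent. Dose normalisation makes this worse. The 9 µg/day value is multiplied by 112/9 = 12.4 and then counts as much as the 112 µg/day value, although it is the one nearest any plausible LLOQ. Entering it as zero lowers the average Css and raises CL and F. A Period 2 SC equivalent computed as infusion dose divided by F would then come out too low.

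The integration rule raises a second, smaller issue. After 12 h the SC samples are 12 to 24 h apart, and a straight line across an exponential decline overstates area. The error depends on the dosing interval, and dosing frequency is something the DLRT chooses from PK data.

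**Working it through.** **The plan's own figure.** At F = 0.25, the SC equivalent of 112 µg/day is 112/0.25 = 448 µg, against 450 stated in Protocol 2.4. The four animal values (0.35, 0.16, 0.21, 0.30) average 0.255. Both agree with the text. The documents give no bias figure for either rule.

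**Expected Css.** Protocol 2.3.1: "The estimated mean clearance, volume of distribution, and terminal half-life were 2.29 L/hour, 4.84 L and 2.47 hours, respectively". With Css = (daily dose/24)/CL:
- 9 µg/day: 0.375/2.29 = 0.164 ng/mL
- 28 µg/day: 1.167/2.29 = 0.509 ng/mL
- 112 µg/day: 4.667/2.29 = 2.04 ng/mL

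Only the first is plausibly BLQ at typical values.

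**Effect of one zero on CL and F.** Let C be the common normalised Css. With k of n values set to zero, the average is C(n−k)/n and CL is multiplied by n/(n−k).
- Run-in samples only: 3/2 = 1.50, so +50%; dose/F is 1/1.5 = 0.67 of its proper value.
- Run-in plus day 30: 4/3 = 1.33, so +33%; dose/F is 0.75 of its proper value.
- In a six-subject cohort (three samples each), the geometric mean F is multiplied by 1.5^(k/6), where k is now the number of affected subjects: 1.07, 1.14 and 1.22 for one, two and three.
- If Css were instead pooled over six subjects × three samples, one zero gives only 18/17 = 1.06.

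**How often.** For assumed LLOQs of 0.05 to 0.10 ng/mL and a lognormal Css with mean 0.164 and assumed CV of 50% to 100%, the share of subjects BLQ at 9 µg/day is 1% (LLOQ 0.05, CV 50%) to 43% (LLOQ 0.10, CV 100%).

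**Zeroing against exclusion.** Simulated three-sample averages with the same LLOQs and an assumed between-subject CV of 50% give these geometric-mean CL biases:

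| Within-subject CV | Zeroed | Excluded |
|---|---|---|
| 0% to 30% | +0.5% to +10% | 0 to −1.5% |
| 50% | +1.9% to +12% | −1.2% to −3.7% |

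A between-subject CV of 100% makes the zeroing bias considerably larger and leaves the exclusion bias about the same.

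**AUC rule.** One-compartment steady-state model on the protocol's last-dose sampling times: 450 µg, F 0.25, elimination half-life 2.47 h, assumed absorption half-life 4 to 12 h, no BLQ values. Bias against F × Dose/CL, integrating only the observed grid:

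| Interval | Linear | Linear-up/log-down |
|---|---|---|
| q12h | −0.7% to −0.4% | −1.2% to −0.5% |
| q24h | +0.5% to +4.6% | −2.0% to −0.9% |
| q48h | +4.0% to +8.5% | −2.1% to −0.9% |
| q72h | +4.7% to +8.6% | −2.1% to −0.9% |
| q96h (samples end at 48 h) | −3.7% to +8.5% | −8.4% to −2.1% |
| q7d (samples end at 96 h) | +4.3% to +8.6% | −2.1% to −1.3% |

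With absorption half-lives of 0.5 to 24 h, and with the 1.46 h half-life implied by ln2 × 4.84/2.29 also tried, the linear rule gives −2.7% to −0.2% for q12h, −1.8% to +5.7% for q24h and −1.8% to +8.6% for q48h and q72h. Linear-up/log-down gives −6.7% to −0.2%.

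**Both rules together on SC samples.** A zeroed SC value mostly lowers AUC.
- Absorption half-life 8 h, LLOQ 0.10 ng/mL: the linear bias falls from +6.4% to +3.9% (q48h), +7.0% to +2.0% (q72h) and +7.0% to +1.7% (q7d).
- Absorption half-life 4 h: the offset is only 0.1 to 0.3 points.
- Absorption half-life 10 h, LLOQ 0.20 ng/mL: q72h goes from +5.7% to −3.0%, so the sign can change.

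**The case against.** The strongest reply is that the one large effect is conditional. The LLOQ and variability are assumed, the 1% to 43% range shows how little is known, and within-subject averaging is a reading of the SAP rather than its stated rule. That is correct, and it is why the effect is given per affected subject and as nil when no infusion sample is BLQ. It does not rescue the rule, because zero is wrong whenever it is applied to a steady-state infusion sample.

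The linear trapezoid is a conventional choice with single-digit bias here, and log-down is not bias-free. That also stands, so a sensitivity analysis would be enough. Nor does F alone set Period 2 dosing: the target regimen comes from the DLT-based MTD or the maximum tested dose. F bears mainly on the SC equivalents of 9 and 28 µg/day, alongside other data.

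Three stronger readings might be inferred and are not supported:
- **That both rules always push F upward.** For q12h, the regimen of Cohorts 1 and 2, the linear rule is slightly low, and zeroed SC values mostly lower AUC.
- **That the zero rule contradicts SAP 9.3**, which says "No data imputation for PK and biomarker data". That section concerns missing and incomplete data. A BLQ result is an assayed sample, so there is no clear contradiction.
- **That zero troughs make the geometric mean of Cmin undefined for q48h to q7d.** SAP 10.7 defines Cmin only for q12h and q24h, and median and range are already planned.

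**Conclusion.** The concern holds in a limited form. Zeroing a BLQ infusion sample inflates that subject's CL and F by 50% or 33%, given within-subject averaging over three or four normalised values. How often this happens depends on an LLOQ the documents do not state. The linear trapezoid adds a modest bias that varies with dosing interval, about −0.5% for q12h and up to about +9% for longer intervals, under a one-compartment model with assumed absorption half-lives of 4 to 12 h. Zeroed SC samples offset part of it. The net direction for F depends on LLOQ, absorption rate and interval, and cannot be called upward in general. The change is worth making because the infusion part is avoidable and F feeds the Period 2 dose derivation.

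**What to change.** In SAP 10.7:
1. Exclude BLQ infusion Css values from the CL average and report how many were excluded. State the LLOQ, whether averaging is within subject, and whether day 30 is included.
2. Limit the zero rule to samples before the first quantifiable post-dose value. Treat BLQ values after the last quantifiable SC sample as missing for AUC and λz.
3. Use linear-up/log-down for AUC, or report it as a sensitivity analysis beside the linear result.
4. State how AUCτ is extrapolated when the last quantifiable sample falls short of the interval. This is unavoidable for q96h, where last-dose sampling ends at 48 h.

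The cost is SAP wording and software settings; no new samples are needed. Exclusion brings a small left-censoring bias in CL, roughly 0 to −3% (−3.7% with a within-subject CV of 50% and an LLOQ of 0.10 ng/mL), which is why the count should be shown. Log-down carries its own small downward bias, which should be acknowledged in the report.
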